**2. Target number of patients**

Target sample size: 100 patients

Immediately after the approval of JIA as an indication for treatment with Humira, all patients who receive Humira for the treatment of JIA affecting multiple joints will be registered, and the data for the first 100 patients will be tabulated and analyzed, and the results reported to the regulatory authority. Registration of patients will be continued until the authority concludes its final evaluation.

<Rationale>

Considering the number of patients for whom registration is considered feasible, we will analyze data for 100 patients to detect ADRs with an incidence of 3% at a probability of 95%.

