#### **3) Information on the efficacy of Humira**

- ① Clinical course
  - DAS28 (number of tender joints and number of swollen joints), global assessment by

patient (VAS), global health by physician (VAS), erythrocyte sedimentation rate (ESR, 1 hr value), and CRP. (Baseline, and Weeks 4, 8, 16, and 24 weeks of treatment)

- Serum MMP-3 level (Baseline, and Weeks 4, 8, 16, and 24 weeks of treatment)
- Anti-CCP antibody (Baseline and 24 weeks of treatment)
- Height and body weight (Baseline, and Weeks 4, 8, 16, and 24 weeks of treatment)

② Factors that may affect the efficacy of Humira

- Summarized efficacy data by patient background factor

4) Matters related to special populations

List of occurrences of ADRs/infections in special populations such as pregnant/lactating women, patients with renal function disorder, and patients with hepatic function disorder

(2) Methods of analysis

Appropriate methods of analysis such as the chi-square test will be used according to the scale and nature of the data analyzed.

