#### 9.13. Test methods

In this analysis plan, a paired t-test should be conducted for the amount of change from before the start of administration. For the incidence rates and remission rates (DAS28) of adverse reactions for each background factor, Fisher's exact test or Mann-Whitney U test should be conducted. Tests should not include an unknown/unspecified category.

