#### 9.14. Level of significance

In principle, the significance level of statistical analyses used in this survey is two-sided 5%.  $p < 0.05$  ( $< 5\%$ ) should be considered significant.

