Purpose of analysis: For DAS28 disease activity in patients whose reason for use and type of disease is polyarthritis (RF negative), a bar graph will be created for DAS28 disease activity before the start of treatment, at 4, 8, 12, 16 and 24 weeks after the start of treatment, and at the final assessment in accordance with “11. Data-layer separation” (reason for use and type of disease” and “12. Handling of data on tests/timing of assessment” (time window for efficacy assessment).

Note: None in particular.

“Figure 3.5.3.5 Remission rates assessed by DAS28-4/ESR by reason for use and type of disease (polyarthritis [RF positive])”

Analysis object: Patients included in the efficacy analysis set

Purpose of analysis: For DAS28 disease activity in patients whose reason for use and type of disease is polyarthritis (RF positive), a bar graph will be created for DAS28

disease activity before the start of treatment, at 4, 8, 12, 16 and 24 weeks after the start of treatment, and at the final assessment in accordance with “11. Data-layer separation” (reason for use and type of disease” and “12. Handling of data on tests/timing of assessment” (time window for efficacy assessment).

Note: None in particular.

“Table 3.6.1 Changes in CDAI”

Analysis object: Patients included in the efficacy analysis set (CDAI)

Purpose of analysis: For CDAI, the basic statistics of values measured before the start of treatment, at 4, 8, 12, 16 and 24 weeks after the start of treatment, and at the final assessment will be calculated in accordance with “12. Handling of data on tests/timing of assessment” (time window for efficacy assessment). Basic statistics will also be calculated for the amount of change from before the start of treatment, and a paired t-test will be conducted.

Note: None in particular.

“Table 3.6.2 Changes in SDAI”

Analysis object: Patients included in the efficacy analysis set (SDAI)

Purpose of analysis: For SDAI, the basic statistics of values measured before the start of treatment, at 4, 8, 12, 16 and 24 weeks after the start of treatment, and at the final assessment will be calculated in accordance with “12. Handling of data on tests/timing of assessment” (time window for efficacy assessment). Basic statistics will also be calculated for the amount of change from before the start of treatment, and a paired t-test will be conducted.

Note: None in particular.

“Table 3.7 Trends in other efficacy endpoints”

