Analysis object: Patients included in the efficacy analysis set

Purpose of analysis: For tender joint count, swollen joint count, VAS assessed by the patient, VAS assessed by a doctor, ESR, CRP, serum MMP-3 concentration, height and weight, the basic statistics of values measured before the start of treatment, at 4, 8, 12, 16 and 24 weeks after the start of treatment, and at the final assessment will be calculated in accordance with “12. Handling of data on tests/timing of assessment” (time window for efficacy assessment). Basic statistics will also be calculated for the amount of change from before the start of treatment, and a paired t-test will be conducted.

Note: None in particular.

“Table 4.1 List of patients excluded from the safety analysis set and patients excluded from the efficacy analysis set of special drug use-results surveys, etc. (including reasons for exclusion)”

Analysis object: Patients excluded from the safety analysis set, patients excluded from the efficacy analysis set

Purpose of analysis: A list of case numbers for patients excluded from the safety analysis set and patients excluded from the efficacy analysis set, and patients for whom the reason for exclusion was output will be created.

Note: Where one patient has more than one reason for exclusion, they should be linked with commas when output.

“Table 4.2 List of patients”

Analysis object: Patients with fixed CRFs

Purpose of analysis: A list of patients analyzed will be created for the following items:

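### SAP Table 3.7 tests raw height and weight against zero change as efficacy endpoints; in growing children zero is not the no-effect value, so the p-values do not address a Humira effect

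*SAP*

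**What the plan says.** SAP Section 13.3 (Efficacy) includes "Table 3.7 Trends in other efficacy endpoints". Its variable list runs from joint counts, both VAS scores, ESR and CRP to "serum MMP-3 concentration, height and weight, the basic statistics of values measured". Values are summarised before treatment, at weeks 4, 8, 12, 16 and 24, and at the final assessment. Then: "Basic statistics will also be calculated for the amount of change from before the start of treatment, and a paired t-test will be conducted". The note to the table adds nothing.

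This follows the general rule in SAP Section 9.13, by which "a paired t-test should be conducted for the amount of change from before the start of administration". SAP Section 9.14 sets a two-sided 5% level and says that p < 0.05 "should be considered significant".

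The protocol also files these variables under efficacy. Section 9(1)3), clinical course, lists "Height and body weight (Baseline, and Weeks 4, 8, 16, and 24 weeks of treatment".

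Neither document applies an age- and sex-standardised score, a growth reference, an expected-growth null, an age restriction or a comparator to this test.

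**The concern.** A paired t-test of change from baseline asks whether the mean change differs from zero. That is useful only if zero is what would be seen without an effect. For height and weight in growing children it is not, because both rise with time alone. The SAP expects such children: Section 11 has age layers below 6, 6 to under 11 and 11 to under 16 years, and weight layers below 15 kg and 15 to under 30 kg. With no control group, nothing in the test separates growth from a drug effect.

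The table yields 2 variables × 6 time points (five visits plus the final assessment) = 12 such p-values under an efficacy heading. A small one can be misread as benefit. The test could also be significant while growth is slower than expected, since any clear rise above zero is enough.

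**Working it through.** **Figures in the plan.** There is no power, effect size or SD for height or weight. The only sample-size figure concerns adverse drug reactions (Protocol Section 2: "Target sample size: 100 patients", 3% incidence, 95% probability). It reproduces, 1 − 0.97^100 = 0.952, but has no bearing on this test.

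**Inputs from the documents.** Two-sided 5% level (SAP 9.14); 24-week observation (Protocol 8(1)); target of 100 patients. Missing values are not imputed (SAP 9.1), so n at a visit can be below 100; I use n = 30 to 100.

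**Assumptions (not in the documents).** Height growth 4 to 7 cm/year with SD of 24-week change 0.8 to 2.5 cm; weight gain 2.5 kg/year with SD of change 1 to 3 kg; measurement SD 0.7 cm in patients past growth; no drug effect.

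**Method.** Mean change m = rate × weeks/52. Noncentrality d = m/(SD/√n). The probability of p < 0.05 comes from the noncentral t distribution with n − 1 degrees of freedom.

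**1. Height, week 24, all growing.** m = 4 × 24/52 = 1.85 cm to 7 × 24/52 = 3.23 cm.

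| Rate (cm/year) | SD (cm) | n | d | P(p < 0.05) |
|---|---|---|---|---|
| 4 | 2.5 | 30 | 4.0 | 0.97 |
| 4 | 2.5 | 100 | 7.4 | 1.00 |
| 7 | 0.8 | 30 | 22.1 | 1.00 |
| 7 | 0.8 | 100 | 40.4 | 1.00 |

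The smallest mean rise that reaches p < 0.05 at n = 100 is 1.984 × SD/10, which is 0.16 cm at SD 0.8 and 0.50 cm at SD 2.5.

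**2. Height, week 24, only 30% growing.** Mean = 0.3m. Variance = 0.3·SD² + 0.7·0.7² + 0.3·0.7·m². For 4 cm/year and SD 2.5: mean 0.55 cm; variance 1.875 + 0.343 + 0.716 = 2.93; SD 1.71; d at n = 100 = 3.2; probability 0.89. With SD 0.8 the overall SD is 1.12, d = 5.0 and the probability is above 0.99. At 7 cm/year it is above 0.99 for either SD. At n = 30 and 4 cm/year it falls to 0.40 (SD 2.5) and 0.75 (SD 0.8). The calculation treats the mixture as normal, so these are approximations.

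**3. Height, week 4.** Take 5 cm/year, between-child SD 30% of growth and measurement SD 0.7 cm. Then m = 5 × 4/52 = 0.38 cm and SD = √(0.115² + 0.7²) = 0.71 cm. All growing: 0.82 (n = 30) to 1.00 (n = 100). With 30% growing: 0.13 to 0.35.

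**4. Weight, all growing.** m = 2.5 × 24/52 = 1.15 kg at week 24 and 2.5 × 4/52 = 0.19 kg at week 4.

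| Week | SD (kg) | n = 30 | n = 100 |
|---|---|---|---|
| 24 | 1 | 1.00 | 1.00 |
| 24 | 2 | 0.86 | 1.00 |
| 24 | 3 | 0.53 | 0.97 |
| 4 | 1 | 0.17 | 0.48 |
| 4 | 3 | 0.06 | 0.10 |

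**5. Slowed growth.** Halving 4 cm/year gives m = 2 × 24/52 = 0.92 cm. At n = 100 the test still reports a significant increase with probability 0.96 (SD 2.5) to 1.00 (SD 0.8).

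**The case against.** The case on the other side has four parts.

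- **The population may not all be growing.** Protocol Section 3 sets no upper age limit, the SAP age layers run to 21 and over and to 65 and over, and Table 2.13 reports patients aged 15 or more separately. This stands. It limits how certain a significant result is, especially in small samples, but it does not make zero the right null for those who are growing.
- **Nothing hangs on these p-values.** The SAP defines efficacy by EULAR response and remission (Section 10.3). Height and weight enter neither, Table 3.7 is headed as trends, and the sample size comes from adverse reactions. This stands and makes the point minor.
- **Every paired t-test in a single-arm survey has the same limit.** It is true that none of them isolates a drug effect. Height and weight are still the clearer case, because growth gives them a predictable upward drift that ESR or CRP do not have.
- **Growth is not a stated purpose of the survey.** Correct, and so the point is not that a growth analysis is missing. It is that the test planned for these two variables does not inform efficacy.

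A reader might infer that height and weight will be significant whatever the drug does. The documents do not support that: they give no age mix, growth rate or SD, and the probabilities for weight, and for height at week 4, can be well below 1. A reader might also infer that significance is assured even in very small groups. At n = 10, 4 cm/year and SD 2.5 cm, t at the expected mean is 2.34 (p = 0.044), but the probability of reaching p < 0.05 is only about 0.55. Nor does the SAP say that a significant change in height or weight counts as efficacy; Section 9.14 only labels it significant.

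**Conclusion.** The point holds in limited form and is minor. Raw height and weight are classed as efficacy endpoints and tested against a null that growth alone makes false in children who are growing, with no comparator. Whether or not p falls below 0.05, the result does not address a Humira effect in those patients.

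On the assumed growth rates and SDs, a significant rise in week-24 height without drug effect is nearly certain at n = 30 to 100 if all patients are growing, and still likely at n = 100 (about 0.9 to 1.0) if 30% are. For week-24 weight with all patients growing it is about 0.5 to 1.0. At week 4 it ranges from little above the nominal 5% for weight to near certainty for height with every patient growing and n = 100. The descriptive statistics in Table 3.7 remain valid, and no efficacy judgement or sample size changes.

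**What to change.** In Table 3.7, remove the paired t-test for height and weight and keep the basic statistics of values and of change from baseline. Add a matching exception to the general rule in SAP Section 9.13. The cost is a line in each place, with no new data and no loss of descriptive information.

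Optional alternative: in patients still growing, test the change in age- and sex-standardised height and weight scores, for which zero change is the reference expectation, and summarise the other patients separately. Age, sex, height and weight are already collected. The downside is that it needs an external growth reference and a rule for who counts as still growing, neither of which the documents provide.
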